16.9 Data & Safety Monitoring

16.91 The principal investigator(s) and the study statistician will review the study at least every quarter to identify accrual, adverse events, and any endpoint problems that might be developing. The Mayo Clinic Cancer Center (MCCC) Data Safety Monitoring Board (DSMB) is responsible for reviewing accrual and safety data for this trial at least twice a year, based on reports provided by the MCCC Statistical Office.

16.92 Adverse Event Stopping Rules: The stopping rules specified below are based on knowledge available at study development. We note that the Adverse Event Stopping Rule may be adjusted in the event of either (1) the study re-opening to accrual or (2) at any time during the conduct of the trial and in consideration of newly acquired information regarding the adverse event profile of the treatment(s) under investigation. The study team may choose to suspend accrual because of unexpected adverse event profiles that have not crossed the specified rule below. The following rule will be evaluated for each arm separately.

Accrual will be temporarily suspended if at any time we observe events considered at least possibly related to study treatment (i.e. an adverse event with attribute specified as “possible,” “probable,” or “definite”) that satisfy one of the following:

- If 3 or more patients in the first 15 treated patients experience a grade 3 or higher adverse event, besides acute dermatitis, that is at least possibly related to treatment within 90 days post treatment..
- After the first 15 patients have been treated: if $\geq 20\%$ of all patients experience a grade 3 or higher adverse event, besides acute dermatitis, that is at least possibly related to treatment within 90 days post treatment.

Similarly, within each of the modalities (photon, proton, or brachytherapy APBI), accrual will be suspended for that modality:

- If 6 or more patients in the first 30 treated patients experience a grade 3 or higher adverse event at least possibly related to treatment at any time after 6 months following completion of the protocol treatment.
- After the first 30 patients have been treated: if $\geq 20\%$ of all patients experience a grade 3 or higher adverse event at least possibly related to

treatment at any time after 6 months following the completion of protocol treatment.

We note that we will review grade 4 and 5 adverse events deemed “unrelated” or “unlikely to be related”, to verify their attribution and to monitor the emergence of a previously unrecognized treatment-related adverse event.

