Proton beam APBI is a particularly promising alternative to other forms of APBI. Like 3D-CRT APBI delivered with photons, it is noninvasive and has less dosimetric inhomogeneity compared with brachytherapy delivery methods.²⁴ Due to unique physical properties of protons including their characteristic Bragg Peak, protons can be directed to treat deep-seated tumors while significantly sparing surrounding normal tissue, resulting in improved dose conformity. The Massachusetts General Hospital group recently reported long-term outcomes of their initial clinical experience with proton APBI on a phase 1 dose-escalation trial.²⁵ Patients with unifocal, T1 tumors with tumor-free margins of ≥ 2 mm and pathologically negative axillary nodes were eligible. The dose was 32Gy in 8 fractions given twice daily and could be delivered with either protons, photons, or mixed photons and electrons. At 7 years, the local failure rate for all 98 evaluable patients was 6%. Physician rated cosmesis was good or excellent in 94% of photon patients, compared with 62% among the 19 patients treated with protons ($p=0.03$). Similarly, skin toxicity was more common in the proton group. The higher than expected level of skin toxicity is likely a result of suboptimal dose, beam arrangement and number of beams.²⁴ For example, a single field was used each fraction in the proton arm in order to minimize machine time. In contrast, Bush et al. from Loma Linda recently reported very favorable cosmetic and toxicity outcomes in 100 patients treated on a phase II study of proton APBI.²⁶ Eligibility included non-lobular carcinoma of the breast, pathologically negative margins by at least 2mm, and primary tumors ≤ 3 cm. In this study, 40Gy was delivered in 10 daily fractions over 2 weeks and multiple fields were treated each day. With a median follow-up of 5 years, good or excellent cosmesis was noted in 90% of patients by both physician and patient reports. There was no acute or late grade 3 skin toxicity. Grade 1 telangiectasias were seen in just 7% of patients. The 5 year ipsilateral breast tumor recurrence-free survival was 97%.

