8.2 Radiation Therapy Adverse Events

The descriptions and grading scales found in the revised NCI Common Terminology Criteria for Adverse Events (CTCAE), version 4 will be utilized for grading all adverse events. All appropriate treatment areas should have access to a copy of the CTCAE, v. 4. A copy of the CTCAE, v. 4 can be downloaded from the CTEP web site
 (██████████).

EVENTS EXPECTED

Erythema, dry desquamation, hyper or hypopigmentation are anticipated to occur commonly. Some patients may develop moist desquamation, which usually heals within 2-3 weeks. Mild swelling of the breast or mild breast pain are also likely side effects of treatment. It is not anticipated that treatment breaks should be needed, as severe acute toxicities are extremely rare.

Transient, persistent, and occasionally symptomatic seroma formation can occur and will be monitored for during treatment and at follow-up. Telangiectasia, and chronic changes in pigmentation can also commonly be seen, as can soft tissue fibrosis.

Infection is less likely, occurring in less than 10% of patients, generally following brachytherapy.

Skin or subcutaneous toxicity requiring surgery, pneumonitis, rib fractures, or any grade 3 or greater complications including pain are uncommon after ABPI, and are expected to occur in <10% of patients

Patients will also undergo venipuncture as part of the study. Risks of that procedure include hematoma, swelling, tenderness and inflammation at the site, persistent bleeding, vasovagal response, and rarely thrombosis and infection.

Method of detection, signs and symptoms, and method of treatment will be reported for all detected toxicities

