If the increase in APBI adverse cosmesis rate from baseline is 5.0%, there is a 98.4% chance of concluding that the APBI adverse cosmesis increase from baseline is acceptable; this drops to 72.8% if the true rate is 10%, and further drops to 49.6% if the true rate is 15%. If the increase in APBI adverse cosmesis rate from baseline at 3 years is 20% or greater, we are most likely to recommend no further investigations, and conclude that the increase in APBI adverse cosmesis rate is unacceptably high.

Other considerations: Adverse events, quality/duration of response, and patterns of treatment failure observed in this study, as well as scientific discoveries or changes in standard care will be taken into account in any decision to terminate the study.

16.43 Preliminary Analysis: The preliminary analysis is to examine whether the data from the three methods (photon, proton and brachytherapy PBI) can be combined by assessing any difference in the safety profile and baseline patient and tumor characteristics. We will conclude that the variability in the three samples is acceptable and proceed to the primary analysis if all the following conditions are met:

- The difference in rate of grade 3 toxicity between the groups is $\leq 10\%$.
- There is not a significant difference in the rate of IBTR between the groups (using pair-wise chi-squared tests with Bonferroni correction for multiple comparisons).
- The distribution of African Americans and the percentage of cytotoxic chemotherapy use between the groups is not significantly different (using pair-wise chi-squared tests with Bonferroni correction for multiple comparisons).
- The distribution of age between the groups is not significantly different (p -value ≥ 0.05 using a Tukey's test). The difference in age in 10 increments (50-59, 60-69, and ≤ 70) will be reported.
- Tumor size will be dichotomized to two categories ($\leq 1\text{cm}$ vs $1\text{-}2\text{cm}$). The percentage of larger tumor ($1\text{-}2\text{cm}$) between the groups is not significantly different (using pair-wise chi-squared tests with Bonferroni correction).

If any of the above conditions are failed to be met, we will only report the safety and efficacy of each individual arm as secondary and exploratory endpoints.

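### Section 16.92: the 90-day suspension rule exempts acute dermatitis at every grade, so related grade 4-5 dermatitis never counts toward the automatic trigger

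*Combined protocol and SAP*

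**What the plan says.** Section 16.92 has two early bullets, applied to each arm separately. The first is met by 3 or more of the first 15 treated patients; the second applies once 15 have been treated and is met by at least 20% of patients. Both count the same event, with onset within 90 days: "grade 3 or higher adverse event, besides acute dermatitis, that is at least possibly related to treatment". Both carry the same exemption, and neither limits it by grade.

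Two late bullets, applied within each modality, have no dermatitis exemption (6 or more of the first 30, then at least 20%). They count only events more than 6 months after treatment.

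A closing note in 16.92 says "we will review grade 4 and 5 adverse events deemed" unrelated or unlikely to be related, in order to verify attribution and to notice a previously unrecognised treatment effect.

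On expected toxicity, section 8.2 says treatment breaks should not be needed, "as severe acute toxicities are extremely rare", and that "any grade 3 or greater complications including pain are uncommon after ABPI", with an expected frequency below 10%.

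Section 16.43 sets conditions for pooling the three techniques in the primary analysis. The first is: "The difference in rate of grade 3 toxicity between the groups is" at most 10%. It gives no wording for higher grades, no time window and no attribution requirement.

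**The concern.** An exemption makes sense for a reaction expected to be frequent and manageable, because counting it would trip the rule without telling anyone anything new. That reasoning does not reach the top of the grading scale. As worded, the rule counts any related grade 3 event other than acute dermatitis, but not a related grade 4 or 5 acute dermatitis, so a less severe event counts where a more severe one does not. No other counted rule closes the gap: the late bullets start too late, and the closing note concerns events judged unrelated or unlikely.

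At stake is whether accrual pauses automatically if this once-daily, large-fraction regimen causes severe early skin reactions in one arm. Otherwise the pause depends on someone deciding to call it.

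A separate wording question affects the primary analysis. If any condition in 16.43 fails, the pooled analysis is replaced by arm-by-arm reporting as secondary and exploratory endpoints. That decision should not depend on whether two words were left out.

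**Working it through.** The plan states no error rate or power for the suspension rule or the pooling check, so there is no figure of its own to reproduce. The thresholds do agree with each other: 3/15 = 6/30 = 20%, the same as the continuation rules.

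**1. What the early rule counts.** Counted events = related grade 3+ events within 90 days, minus acute dermatitis of any grade.
- Suppose 3 of the first 15 women in an arm have related grade 4 acute dermatitis and nothing else. Count = 3 − 3 = 0. The trigger is 3, so there is no suspension.
- If only grade 3 dermatitis is exempt, count = 3 and 3/15 = 20%. The rule is met.

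**2. The exemption's window.** Section 16.3 defines acute as the first month after radiotherapy; 16.61 defines it as up to 90 days. Dermatitis arising on days 31-90 is exempt under 16.61 but counts under 16.3.

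**3. What limiting the exemption would do to the trigger.** Let q be the per-patient rate of other qualifying events and d the rate of grade 4-5 acute dermatitis, in different patients. Both are assumptions. The documents give no value for d, and 8.2 gives only an expectation below 10% for grade 3 or greater complications, so q is shown at 5% and 10%.

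P(3 or more of 15) = 1 − Σ(k = 0 to 2) C(15,k) p^k (1−p)^(15−k)

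with p = q under the present text and p = q + d if grade 4-5 dermatitis counts.

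| d | q = 5%, present | q = 5%, counted | q = 10%, present | q = 10%, counted |
|---|---|---|---|---|
| 1% | 3.6% | 5.7% | 18.4% | 22.4% |
| 2% | 3.6% | 8.3% | 18.4% | 26.5% |
| 5% | 3.6% | 18.4% | 18.4% | 39.6% |
| 10% | 3.6% | 39.6% | 18.4% | 60.2% |

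The present-text columns do not move with d: the rule cannot respond to this toxicity, however common it is. If d is close to zero, as 8.2 implies, the two versions nearly coincide.

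**4. The pooling condition.** Section 16.44 plans 40 to 60 patients per technique. The smallest counts that exceed a 10-point difference against zero are:
- n = 40: 4/40 = 10.0% does not exceed the limit; 5/40 = 12.5% does.
- n = 60: 6/60 = 10.0% does not; 7/60 = 11.7% does.

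If those events are all grade 4-5 and grade 3 is read literally, the difference is 0 − 0 = 0 points and the condition passes. Counted as grade 3 or higher, it fails. Sections 8.2 and 16.92 write grade 3 or greater/higher, and 16.62 writes grade 3 or 4, so the bare wording in 16.43 stands out.

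**The case against.** The best reply is that these events would not go unnoticed, and that is right. Radiation dermatitis is graded at baseline and at every evaluation (10.4). Events meeting the serious definition in 10.1 are reported and followed up (10.3, 10.51), and a serious, related, unanticipated event goes to the IRB within 5 working days. The investigators and statistician review the study at least quarterly, and the DSMB at least twice a year (16.91). Section 16.92 lets the team suspend accrual below the threshold and adjust the rule at any time. A reader might infer that severe skin toxicity is unmonitored; the documents do not support that. What remains is that none of these is a counted trigger.

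A reader might also take the closing note on grade 4-5 events to mean that related ones get less attention. Its stated purpose is to check attribution, so it shows no such thing; it simply does not fill the gap.

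Section 1.2 reports an earlier series in which "skin toxicity was more common in the proton group", and a reader might infer that severe acute dermatitis is to be expected here. The section does not support this. It attributes the excess to suboptimal dose and beam arrangement, and then describes 100 proton patients with no acute or late grade 3 skin toxicity. This protocol also requires at least two proton beams and limits skin dose (7.13).

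Some exemption is reasonable, since 8.2 expects erythema and dry desquamation commonly and moist desquamation in some patients. That does not explain leaving out its upper limit.

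Finally, grade 3 toxicity in 16.43 may be shorthand for grade 3 or higher. That is possible, and the 5/40 example is an illustration that no document predicts. Toxicity by maximum grade would still be tabulated (16.61, 16.62) and compared across techniques (16.7).

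**Conclusion.** The main point holds on the face of the text. Related grade 4-5 acute dermatitis cannot contribute to the 90-day trigger, and 3 of 15 such patients score 0. This is a gap in the wording of one counted rule. It is not a failure of safety oversight as a whole, and it changes no sample size, estimate or error rate. If 8.2 is right about rarity, the practical effect is small; the probabilities in the table rest on assumed rates and only illustrate the rule's insensitivity.

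The unclear meaning of acute is a plain inconsistency between 16.3 and 16.61, and it affects who is exempt on days 31-90.

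The point about 16.43 is secondary and conditional: it matters only if grade 3 is applied literally. The correction is worthwhile because it costs almost nothing and the pooled primary analysis depends on the condition.

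**What to change.** 1. In both 90-day bullets of 16.92, limit the exemption so that it does not remove grade 4-5 dermatitis from the count, for example 'besides grade 3 acute dermatitis'. This concerns trial-level accrual monitoring, not the management of individual patients.
2. Reconcile the one-month definition of acute in 16.3 with the 90-day definition in 16.61, and state in 16.92 which window the exemption uses.
3. In the first condition of 16.43, write 'grade 3 or higher toxicity'.

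No new data are needed, because dermatitis is already graded at each evaluation. The cost is a slightly higher chance of a temporary suspension (for example, from 3.6% to 5.7% in the first 15 patients at the assumed rates q = 5% and d = 1%) and a slightly higher chance that the pooling condition fails.

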16.61 *Acute adverse events (up to 90 days post-RT):* All patients who were registered to the study and started treatment will be included in the acute adverse event analysis. An acute adverse event is an AE, regardless of attribution, that occurs up to 90 days post-RT. The maximum grade for each type of acute AE will be recorded for each patient. Data will be summarized as frequencies and relative frequencies. Additionally, the relationship of the adverse event(s) to the study treatment will be taken into consideration.

16.62 *Late adverse events:* All patients who were registered to the study and started treatment will be included in the late adverse event analysis. A late adverse event is an AE, regardless of attribution, that occurs at least 90 days post-RT and up to 3 years post-RT. The maximum grade for each type of late AE will be recorded for each patient. Data will be summarized as frequencies and relative frequencies. Additionally, the relationship of the adverse event(s) to the study treatment will be taken into consideration. Prior APBI reports have suggested rates of grade 3 or 4 toxicity to be $\leq 10\%$.^{18,47,55,56}

16.63 *Quality of life:* The QOL measurements will be summarized at each time point as mean \pm SD and median (minimum value, maximum value). Changes in the QOL measurements from baseline will be determined at each follow-up measurement. These will be displayed as spaghetti plots. The assessment of the changes at each time point will be done with a paired t-test or Wilcoxon signed rank test, whichever is appropriate.

16.64 *Cosmesis*: The values of the cosmesis instruments (patient self-reported and panel-assessed) will be summarized with the frequencies of fair or poor cosmesis events at baseline and 3 years, and the difference at 3 years, as well as their relative exact binomial confidence intervals.

16.65 *IBTR incidence*: The IBTR cumulative incidence will be estimated using a competing risks method (Gooley et al.). The competing risks will be regional/distant breast cancer recurrence and death.

16.66 *Regional recurrence incidence*: The regional breast cancer recurrence cumulative incidence will be estimated using a competing risks method (Gooley et al.). The competing risks will be local/distant breast cancer recurrence and death.

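### The two numeric accrual-suspension rules in 16.92 leave about day 91 to day 183 uncovered, so a related grade 3+ event that begins and ends there counts under neither

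*Combined protocol and SAP*

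**What the plan says.** Section 16.92 sets two pairs of numeric suspension rules. Both are restricted to "events considered at least possibly related to study treatment" and both are applied by arm or modality.

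- **Early pair.** The initial trigger is "If 3 or more patients in the first 15 treated patients experience a grade 3 or higher adverse event, besides acute dermatitis", for an event "that is at least possibly related to treatment within 90 days post treatment". After 15 patients the trigger becomes 20% or more of all patients, over the same window.
- **Late pair.** The initial trigger is "If 6 or more patients in the first 30 treated patients experience a grade 3 or higher adverse event at least possibly related" to treatment, occurring "at any time after 6 months following completion of the protocol treatment". After 30 patients the trigger is again 20% or more, for events related to "treatment at any time after 6 months following the completion of protocol treatment". Acute dermatitis is not excluded here.

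For analysis, 16.61 defines acute events as those up to 90 days after radiotherapy, and 16.62 defines a late event as one that "occurs at least 90 days post-RT and up to 3 years post-RT". Section 16.3 places the acute/late boundary at 1 month instead.

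Outside the numeric rules, 16.92 adds: "The study team may choose to suspend accrual because of unexpected adverse event profiles that have not crossed the specified rule below". Section 16.91 provides quarterly review by the investigators and statistician, and Data Safety Monitoring Board review at least twice a year.

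**The concern.** The regimen is described as novel, and the 16.92 rules are the only points at which a stated number of toxicities obliges the study to suspend accrual. The early rule closes at 90 days and the late rule does not open until 6 months, with no reason given for the interval between. Both pairs of analysis definitions, in 16.3 and in 16.61/16.62, run from acute to late without a break, so the gap exists only in the suspension rules.

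Followed to the letter, the plan could accumulate related grade 3+ events at its own 20% threshold within one modality and not be required to pause.

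**Working it through.** **1. The stated thresholds.** Early trigger: 3/15 = 20%. Late trigger: 6/30 = 20%. Both agree with the 20% used after the initial cohorts. The documents give no operating characteristics for these rules.

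**2. Length of the gap.** Six months = 6 × 365.25/12 = 182.6 days. The uncovered time is 182.6 − 90 = 92.6 days, about day 91 to day 183. As a share of the first six months, that is 92.6/182.6 = 51%.

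**3. A worked case.** Suppose six of the first 30 patients in one modality have related grade 3+ events on days 100, 120, 130, 140, 150 and 170, each resolved before month 6.

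- Events at or before day 90: 0, so the early rule counts none.
- Events after day 182.6: 0, so the late rule counts none.
- Related grade 3+ events after day 90: 6 of 30 = 20%, which would meet the late trigger if that interval were counted.

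**4. Share of late events in the gap.** The late window in 16.62 runs from 90 days (about 3 months) to 36 months, which is 33 months. The gap is 3 of those months. Under a constant hazard, 3/33 = 9.1%. The constant hazard is an assumption; the documents give no timing of events.

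**5. Effect of covering the gap on the late trigger.** Suppose the true risk of a related grade 3+ event after month 6 is 10%, and the risk in the gap is g, independent of it (both assumed). If the gap were counted under the late rule, the per-patient probability would be p = 1 − (1 − 0.10)(1 − g). The chance of meeting the initial trigger is P(X ≥ 6), with X binomial (30, p).

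| Assumed gap risk g | p | P(X ≥ 6 of 30) |
|---|---|---|
| 0% (also the rule as written) | 0.100 | 7.3% |
| 1% | 0.109 | 10.1% |
| 5% | 0.145 | 26.2% |
| 10% | 0.190 | 51.7% |

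The existence of the gap does not depend on these rates. They show only what closing it might cost.

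**The case against.** The strongest reply is that oversight does not lapse in the gap. Events are recorded, enter the late analysis in 16.62, and reach quarterly and Board review. Section 16.42 lets adverse events inform any decision to terminate the study, and 16.92 allows the rule itself to be adjusted at any time. An analysis window and a monitoring trigger may also legitimately differ. All of this stands, and it limits the consequence. It does not supply a numeric trigger: under these provisions suspension is a choice, whereas crossing a rule makes it mandatory.

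Three stronger readings are tempting, and the documents do not support them.

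- **That a gap event can never trigger a rule.** The late rule counts patients who experience an event after 6 months, without requiring onset after 6 months, and toxicities are re-graded at each evaluation (10.4). Fibrosis that began in the gap and is still grade 3 at 12 months could count. The gap is strict only for events that start and resolve, or are fatal, within it.
- **That discretionary suspension excludes expected effects occurring too often.** Section 10.1, in the context of reporting unanticipated problems, equates unanticipated with unexpected and includes increased frequency or severity. Section 8.2 gives reference rates (infection below 10%, grade 3+ complications below 10%). The discretionary clause can reasonably be read to cover excess frequency.
- **That some 40% to 45% of events fall in the gap.** The first visit after the end of treatment is allowed on days 28 to 140 (section 4.0) or days 56 to 112 (section 18.1). The part of each window after day 90 is (140 − 90)/112 = 44.6% or (112 − 90)/56 = 39.3%. These are shares of a visit tolerance, not of events. Section 10.3 records the date an event occurred, so a late visit does not move an earlier event into the gap.

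It is also fair to object that 90 days is not the plan's only boundary, since 16.3 uses 1 month. That inconsistency has to be settled in the same revision.

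**Conclusion.** The point holds in a limited form. No numeric suspension rule in 16.92 covers about day 91 to day 183, and a related grade 3+ event confined to that interval counts under neither rule. Whether a persisting event counts is left open by the wording. This finding rests on the text alone.

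Its size is modest under a constant late hazard, at about 9% of late events. The true share could be higher or lower, because the documents give no event timing. Other review provisions soften the consequence but carry no threshold. The gap is worth closing because it lies in the formal safety boundary of a new regimen and the remedy is a short change of wording.

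**What to change.** Reconcile the windows in 16.92 with each other and with the acute and late definitions in 16.3 and 16.61/16.62, so that every related grade 3+ event after treatment falls under one numeric rule. In the same revision:

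- state whether an event is assigned to a window by onset or by presence;
- state whether the acute-dermatitis exclusion carries over to any newly covered period, since only the early rule has it;
- if the interval is left uncovered on purpose, say so and give the reason.

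Where the boundary falls is for the sponsor to decide. The edit is a phrase or two in the 16.92 bullets, plus alignment of the definitions, and 16.92 already provides for adjusting the rule.

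The cost is a higher chance of temporary suspension. It depends on the true rate in the gap, which the documents do not give. Under the assumed rates above it is small if gap events are rare and substantial if they are common; in the latter case the added suspensions would reflect real toxicity.

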16.44 Accrual time and Study duration: Since 10/1/2012 patients have been treated with brachytherapy APBI using an 8 or 10 fraction regimen and prospectively followed as part of a clinical registry at the Mayo Clinic in Rochester, MN. Patient interest in the procedure has steadily increased, and in the last 3 months, 13 patients have been treated (median 4.3 patients per month), all of whom would be eligible for this study. A similar to increased level of accrual of brachytherapy patients is anticipated during the course of this study as familiarity with this procedure amongst surgical and radiation oncology providers rises. With the addition of the photon APBI alternative for patients, we anticipate an accrual rate of 5 patients per month for the first year until the opening of

the Mayo proton facility, after which an accrual of 8 patients per month is anticipated. Therefore, the accrual period for this study is expected to be approximately 3 years. We plan to open this study at the Mayo Clinic in Scottsdale and Jacksonville which will further enhance accrual. Final analysis may begin approximately 5 years after the trial begins, i.e. as soon as the last patient registered has been observed for at least 24 months. A maximum of 60 patients and a minimum of 40 patients will be enrolled per treatment arm.

16.5 **Primary Analysis:** The primary analysis will be to estimate the percentage difference in patients with adverse cosmesis (fair or poor cosmesis) at 3 years compared to baseline. All patients meeting the eligibility criteria who have signed a consent form and started treatment will be in the primary analysis. The percentage difference in patients with adverse cosmesis will be estimated using a binomial estimator (number of women who had an adverse cosmesis event at 3 years minus number of women who had an adverse cosmesis event at baseline, and then divided by total number of women in the primary analysis) and a 95% exact binomial confidence interval. As mentioned above, the following decisions will be made based on the 95% CI:

- ***The upper bound of the 95% CI lies below 14%:*** APBI adverse cosmesis is acceptable.
- ***The upper bound of the 95% CI lies above 14%:*** No evidence to show that APBI adverse cosmesis is acceptable.

16.6 **Secondary Analyses**

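### The 20%-of-all-patients bullet of the late-toxicity suspension rule (16.92) counts patients who cannot yet have a qualifying event, so during accrual it triggers above 20%

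*Combined protocol and SAP*

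**What the plan says.** Section 16.92 has two bullets for late toxicity. They are applied by modality: "within each of the modalities (photon, proton, or brachytherapy APBI), accrual will be suspended for that modality".

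- First-30 bullet: "If 6 or more patients in the first 30 treated patients experience a grade 3 or higher adverse event at least possibly related to treatment", where the event falls more than 6 months after treatment is completed.
- Percentage bullet: it opens with "After the first 30 patients have been treated: if" and then sets a threshold of at least 20%. The denominator is given only by the words "of all patients experience a grade 3 or higher adverse event at least possibly related to". The window in which an event counts is the same as in the first bullet and is worded here as "treatment at any time after 6 months following the completion of protocol treatment".

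Neither bullet sets a minimum follow-up or an evaluable set, and accrual is not held while patients mature. The text does not say whether the percentage bullet replaces the first-30 bullet or runs beside it. No operating characteristics are given for either.

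Section 16.44 expects 5 patients per month in the first year, until the proton facility opens, "after which an accrual of 8 patients per month is anticipated". It also states "A maximum of 60 patients and a minimum of 40 patients will be enrolled per treatment arm".

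**The concern.** A patient treated within the last 6 months adds one to the denominator of the percentage bullet and can add nothing to the numerator. The bullet's only action is to suspend accrual, so it matters only while such patients are present. Whatever the accrual rate, the observed late-event rate needed among patients who can have an event is above 20%. The faster a modality accrues, the larger the gap.

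At stake is whether the 20% written in the plan is the threshold that the monitoring committee will in fact be applying, and how many more patients are treated in a modality with high late toxicity before the rule reacts.

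**Working it through.** **Stated figure.** 6/30 = 20.0%, so the two bullets share one nominal threshold.

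**Inputs.** Let r be the accrual rate per modality per month. The plan gives no such rate except for brachytherapy, so a range is used, all from 16.44:
- r = 8/3 = 2.67: the planned 8 per month with three modalities open, even split assumed.
- r = 60/36 = 1.67: the maximum of 60 spread over the expected accrual period of about 3 years.
- r = 4.3: the recent brachytherapy experience (13 patients in 3 months).

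**Formula.** With steady entry, and ignoring the few days of treatment, n − 6r patients have passed 6 months when n have been treated. The percentage bullet needs 0.20n events, rounded up. Effective trigger = events needed / (n − 6r).

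| Treated, n | Events needed | r = 1.67 | r = 2.67 | r = 4.3 |
|---|---|---|---|---|
| 30 | 6 | 6/20 = 30% | 6/14 = 43% | about 4 past 6 months: unreachable |
| 40 | 8 | 8/30 = 27% | 8/24 = 33% | 8/14 = 57% |
| 60 | 12 | 12/50 = 24% | 12/44 = 27% | 12/34 = 35% |

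**First-30 bullet.** Its denominator is fixed. All 30 have passed 6 months when n = 30 + 6r: 40 treated at r = 1.67, 46 at 2.67 and about 56 at 4.3. Before that it too needs more than 20% of those who can have an event (at r = 2.67, 6/14 = 43% at 30 treated and 6/24 = 25% at 40). From that point it is a true 6/30.

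**Chance of crossing at a true late rate of 30%, r = 2.67, every event occurring at 6 months:**
- At 30 treated (14 past 6 months): P(Bin(14, 0.3) ≥ 6) = 22% as written. With 14 as the denominator, 3 events suffice: P(Bin(14, 0.3) ≥ 3) = 84%.
- At 56 treated (56 − 16 = 40 past 6 months), percentage bullet alone: P(Bin(40, 0.3) ≥ 12) = 56% as written, against P(Bin(40, 0.3) ≥ 8) = 94% with 40 as the denominator.
- At 56 treated, first-30 bullet alone: P(Bin(30, 0.3) ≥ 6) = 92%.

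**Whole rule, by simulation** (60 patients in one modality, r = 2.67, true rate 30%, continuous monitoring, suspension before accrual ends):
- Events spread over months 6–12: percentage bullet alone about 43%; both bullets in force about 92%; with the denominator limited to patients past 6 months, about 93%.
- Events exactly at 6 months: about 92% with both bullets as written, and about 98% if the restricted denominator is used from 30 treated.
- Events spread over months 6–36: about 10% with or without the change.

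**False suspension at a true 10% rate, r = 2.67.** Both bullets as written: about 7%. Restricted denominator applied from 30 treated: about 11% to 22%, depending on when events occur, because 3 of 14 is enough and P(Bin(14, 0.1) ≥ 3) = 15.8%. Restricted denominator applied only once 30 have passed 6 months: about 8–9%.

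**The case against.** The strongest reply is that the rule has two bullets and only one is diluted. Nothing in 16.92 says that the first-30 bullet lapses at patient 31. A reader who looks at the percentage bullet alone might infer that overall detection at 56 treated falls from 94% to 56%. The documents do not support that: with the first-30 bullet in force, the figure at 56 treated is at least 92%. This part of the reply stands and sets the size of the point.

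It does not remove the point. The plan is silent on whether the first bullet persists. That bullet reaches a true 20% only from about 46 treated at 2.67 per month, or about 56 at 4.3, out of at most 60. It also never counts patients 31 to 60, whom only the percentage bullet covers.

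A second reply is that 16.9 already provides quarterly review by the investigators and statistician, board review at least twice a year, and discretion to suspend without crossing the rule. These are real safeguards, but they do not make the written 20% operate at 20%.

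A third is that the visit schedule limits any repair. Section 18.1 lists observation at 12 weeks, 12 months and then annually, so late events may be recorded only at 12 months. This also stands. The reworded bullet corrects the denominator but not the timing of ascertainment.

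**Conclusion.** The point holds for the percentage bullet. The direction is certain at any accrual rate. The size depends on the rate per modality, which the plan does not fix. Under an even three-way split of 8 per month the effective trigger runs from 43% at 30 treated to 27% at 60. At 1.67 per month it runs from 30% to 24%. At 4.3 per month it cannot be reached at 30 treated.

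For the rule as a whole the consequence is modest, provided the first-30 bullet stays in force: slower detection until about 46 treated (at 2.67 per month) and weak coverage of patients 31 to 60. If the percentage bullet were instead read as replacing the first, the loss would be large (about 43% against 92% in the simulation with events in months 6–12). The text should rule that reading out.

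**What to change.** In 16.92, keep the 20% threshold and make two changes:

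1. State that the first-30 bullet remains in force after 30 patients have been treated.
2. Reword the percentage bullet so that it applies once 30 patients in the modality have passed 6 months after completing treatment, with the denominator being the patients in that modality who have passed 6 months.

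The delayed start matters. Using the restricted denominator from 30 treated would let 3 events in 14 patients suspend a modality, and would raise false suspension at a true 10% rate to as much as about 22% at 2.67 per month.

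The cost is two sentences, a count of patients past 6 months in each monitoring report, and slightly more suspensions (about 7% to 8–9% at a true 10% rate). The gain is also limited. At 4.3 per month the reworded bullet becomes active only at about 56 treated. At any rate it does not rescue detection of events arising well after 12 months. The plan should say so, and should state the rule's operating characteristics under an assumed accrual rate and event timing.
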